14.0 STATISTICAL ANALYSIS METHODS AND SAMPLE SIZE

14.1 Analysis Populations

Intent-to-Treat - The intent-to-treat (ITT) population will be defined as all patients who receive at least one dose of decitabine.

Efficacy-Evaluable - The efficacy-evaluable (EE) population will be defined as all patients who receive at least one cycle of treatment.

Safety - The safety population will be defined as all patients with at least one dose of decitabine.

14.2 Statistical Analysis

14.2.1 Descriptive Analyses

Patient Disposition: The number of patients discontinued, the reasons for discontinuation, and the number of cycles administered will be summarized.

Demographics and Baseline Characteristics: Descriptive summary statistics will be provided for demographic and important baseline characteristics. For continuous variables, the number of patients, mean, standard deviation, median, minimum and maximum will be provided. For categorical variables, the number and percent of patients in each demographic/characteristic category will be summarized.

14.2.2 Primary Endpoint Analysis

The primary end-point of this phase II study is the correlation biomarkers with overall response in AML/MDS patients to decitabine.

We will correlate the presence of patient specific mutations (especially mutations in *DNMT3A*, *IDH1*, *IDH2*, and *TET2*) with overall response rates. Mutation rates in these genes and in other patient-specific genes will be correlated with overall response and their respective 95% confidence intervals will be provided.

Statistical considerations. The relationship between AML/MDS-associated mutations and the responsiveness to decitabine will be described by contingency tables and assessed using Chi-square test or Fisher's exact test as appropriate. The differentially expressed genes between responders and non-responders will be determined using the significance analysis of microarray (SAM). Multivariate logistic regression will also be fit to adjust the potential confounding effects of other demographic and clinical characteristics. The resultant critical *P* values will be corrected for multiple testing. Since the Bonferroni correction is known to be too conservative, a permutation analysis (e.g., 10,000 random assignments for

responsive status) will be used to derive an empirical critical P value. The new critical p-value is the number of permutation tests which yield a lower p-value than the original test divided by the total number of permutation tests.[61]

A power analysis was performed using Chi-square test for the association between mutation and response to decitabine. The frequency of *DNMT3A*, *IDH1/2*, and *TET2* mutations in AML and MDS patients are each between 15% and 30% in multiple cohorts.[29-37] **Table 3** shows the minimal detectable differences of response rates between mutant and wild-type cases, assuming an expected overall 45% CR/CRi rate and 80% power. For an average of 20% frequency of a mutated gene, for example, 100 patients will provide 80% power to detect 30% difference at a 2-sided 0.1 alpha error. The purpose of this study is to determine whether any of these mutations result in a clinically significant association that would warrant pre-treatment testing. We believe that a reasonable cut off would be if at least 30% of clinical response could be attributed to the presence of a specific mutation. However, we anticipate that more power could be achieved as we assess patient groups with combined characteristics (e.g. *DNMT3A* mutation or loss of *DNMT3A* expression). In addition, we

Table 3. Detectable mutation associated response rates (80% power, $\alpha = 0.05$)

Total N	% of patients with a given mutation	Detectable response difference	Sensitivity of mutation to predict response at minimum detectable response difference*
100	15%	0.40	80%
	20%	0.35	75%
	30%	0.30	67%
	40%	0.27	61%
	50%	0.26	58%

* Assuming the overall response rate (CR/CRi) of 45%

expect that the majority of the enrolled 125 patients can be used in the analysis (since all of our molecular information will be acquired within 30 days of enrollment, we anticipate a drop-out rate of 20% or less).

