1.3 Correlative Studies

With exception of the peripheral blood sample collected on Cycle 1 Day 4, all correlative studies will be collected under HRPO# 201011766 (“Tissue Acquisition for Analysis of Genetic Progression Factors in Hematologic Diseases”) that all patients will be concurrently enrolled in. The goals of the correlative studies include:

1. To correlate patient-specific mutations with response to decitabine.
We will perform exome sequencing of each patient’s pre-study bone marrow sample and skin sample. We will determine AML/MDS-associated variants found in the bone marrow, but not skin sample. We will correlate the presence of mutations with response (especially mutations in *DNMT3A*, *IDH1*, *IDH2*, and *TET2*). This study is powered to identify mutations with >80% sensitivity to predict decitabine response if used as a clinical assay.
2. To correlate the velocity and depth of response with response to decitabine.
We will assess tumor burden by allele frequency of patient-specific mutations in bone marrow samples collected pre study, Cycle 1 Day 10±1, Cycle 1 Day 28±4, and Cycle 2 Day 28±4. We will assess mutations in at least 24 recurrently mutated genes (including, but not limited to: *FLT3*, *DNMT3A*, *NPM1*, *TET2*, *WT1*, *IDH1*, *IDH2*, *RUNX1*, *NRAS*, *TP53*, *U2AF1*, *KRAS*, *PHF6*, *MSTP9*, *PTPN11*, *KIT*, *SMC3*, *PRUNE2*, *ETV6*, *CEBPA*, *SMC1A*, *ASXL1*, *STAG2*, *RAD21*) as well as all patient-

specific mutations discovered during exome sequencing. The leukemic allele frequency will be measured using the Illumina MySeq or HiSeq platform using DNA capture by gene specific biotinylated-oligonucleotides. Patient bone marrow samples will be assessed pre-study, Cycle 1 Day 10 \pm 1, Cycle 1 Day 28 \pm 4, and Cycle 2 Day 28 \pm 4 and compared with patient specific skin samples (normal control). The velocity of response will be calculated as the natural log rate of patient-specific mutation allele frequency clearance. Depth of response will be defined as the lowest patient-specific mutation allele frequency in a bone marrow sample. The velocity and depth of tumor response will be correlated to:

- Achievement of clinical CR,
- Time to best response,
- Mutational status,
- Time to disease progression.

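### Minor, cheap improvement: the supporting adjusted logistic regression has no covariate list and no sparse-data method, although about 45 responders and 15–30 carriers per named gene are expected

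*Combined protocol and SAP*

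**What the plan says.** The primary analysis in section 14.2.2 (Primary Endpoint Analysis) is a set of two-way tables of mutation by response, "assessed using Chi-square test or Fisher's exact test as appropriate". The adjusted analysis is one sentence: "Multivariate logistic regression will also be fit to adjust the potential confounding effects of other demographic and clinical characteristics". For multiplicity, a permutation procedure "will be used to derive an empirical critical P value".

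The sizing text in the same section works with 100 evaluable patients out of 125 enrolled, "assuming an expected overall 45% CR/CRi rate and 80% power". The named genes (DNMT3A, IDH1/2, TET2) are placed as follows: "mutations in AML and MDS patients are each between 15% and 30% in multiple cohorts". Section 14.2.3 uses the matching split of 45 responders and 55 non-responders.

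Testing goes beyond the named genes: "Mutation rates in these genes and in other patient-specific genes will be correlated with overall response". Section 1.3 adds: "We will assess mutations in at least 24 recurrently mutated genes". Frequencies for these other genes are not given.

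The plan gives no covariate list or limit, no penalized or exact estimator, no minimum carrier count, and no rule for an estimate that is not finite.

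**The concern.** Maximum-likelihood logistic regression is biased away from an odds ratio of 1 when there are few events per coefficient. It has no finite estimate when every carrier responds, or none does. Both conditions are plausible here. Responders number about 45, the number of covariates is open, and the gene list extends to mutations likely to be rarer than 15%.

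The adjusted estimate has some weight. Section 3.1 admits AML at 60 or over, relapsed AML and symptomatic MDS, so confounding by disease group is credible and readers will look at the adjusted odds ratio. The question in section 14.2.2 is whether an association is large enough to justify testing before treatment, which is a question of effect size. For a rare gene, the fit fails most often when the effect is strongest. Reporting only the fits that converge would then drop the most striking results.

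**Working it through.** **Inputs.** From the plan: N = 100; 45% response, so 100 × 0.45 = 45 responders; carriers 15–30%; the Table 3 differences of 0.40, 0.35 and 0.30 at 15%, 20% and 30% carriers; and the worked example of a 0.30 difference at 20% carriers with two-sided alpha 0.1. Assumed, because the plan is silent: 3 to 10 covariates, independent of the mutation; rare genes at 5–10% carriers; 85% response among those carriers.

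**Reproducing the plan's figure.** In the worked example (20 carriers, 80 non-carriers, overall rate 45%), the carrier rate is 0.45 + 0.8 × 0.30 = 0.69 and the non-carrier rate 0.45 − 0.2 × 0.30 = 0.39. The pooled-variance chi-square approximation gives 79.3% power, against 80% stated. The inputs are therefore read correctly.

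**Converting differences to odds ratios.** With frequency f and difference d, p1 = 0.45 + (1 − f)d and p0 = 0.45 − f·d. For f = 0.20 and d = 0.35, p1 = 0.73 and p0 = 0.38, so OR = (0.73/0.27)/(0.38/0.62) = 4.41. The others follow in the same way.

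**Responders per coefficient.** One gene plus 3, 6 or 10 covariates: 45/4 ≈ 11, 45/7 ≈ 6.4, 45/11 ≈ 4.1.

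**Bias of ordinary maximum likelihood.** Simulation with 1,500–2,000 trials per setting, each covariate with log-OR ±0.4, finite fits only. Entries are the mean bias of the log-OR:

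| Carriers, difference | True OR | 3 covariates | 6 covariates | 10 covariates |
|---|---|---|---|---|
| 15%, 0.40 | 5.88 | +7% | +11% | +18% |
| 20%, 0.35 | 4.41 | +8% | +10% | +21% |
| 20%, 0.30 | 3.48 | +9% | +13% | +18% |
| 30%, 0.30 | 3.45 | +6% | +9% | +17% |

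A separate simulation of 1,000 trials per setting gave +6 to +8% with 3 covariates, +9 to +13% with 6 and +15 to +17% with 9. On the odds-ratio scale, 8% on ln 4.41 = 1.484 gives exp(1.484 × 1.08) ≈ 4.97; 21% gives exp(1.484 × 1.21) ≈ 6.02. With no true effect the bias is about zero. Firth's method kept the bias within about 3% at these frequencies, with equal or lower root mean squared error.

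**How much that bias matters.** With three covariates of no effect, the 20% gene (OR 4.41) has bias +0.10 log units against a standard deviation of 0.63, a ratio of 0.16. Across settings the bias stays under a third of a standard error, and Wald coverage is about 92–98%.

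**Failure of the fit.** Given m carriers with response probability p, a zero cell has probability p^m + (1 − p)^m. Averaging over m ~ Binomial(100, f), given at least one carrier, with p = 0.85:

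| Carrier frequency | Probability of a zero cell |
|---|---|
| 10% | 22% |
| 7% | 35% |
| 5% | 48% |

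Simulated failure rates agree: about 21–22% at 10% carriers, 32–34% at 7% and 46–49% at 5%. For the named genes at the plan's own effect sizes, failure is 0 to about 4%.

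**What Firth does for very rare genes.** At 5% carriers with 90% carrier response (true OR 12.1, 6 covariates), ordinary fits failed in 55% of trials, and those that converged had median OR 6.5. Firth gave a finite estimate every time, with median OR 8.4 and mean log-OR about 16% below the truth.

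**The case against.** The strongest reply is that most of the size comes from assumptions. The sentence speaks of demographic and clinical characteristics and does not say the other genes enter the same model, so four to seven responders per coefficient is not a documented figure. With three covariates the ratio is about 11 and the bias small beside the standard error. The regression is supporting. The sizing, Table 3 and the stated 30% cut-off rest on chi-square tests and response differences. Fisher's test already serves sparse unadjusted tables. Nothing names a Wald test, and ordinary maximum likelihood is inferred from silence.

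All of this stands, and it makes the point minor. It does not remove it. Fisher's test does not repair an adjusted odds ratio, and permutation corrects P values, not estimates. A short covariate list alone helps but leaves some bias: if disease group has three levels, as section 3.1 suggests, with age linear and cytogenetic risk in two or three levels, the covariates take 2 + 1 + 1 = 4 or 2 + 1 + 2 = 5 coefficients, between the 3- and 6-covariate columns.

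A reader might infer that the primary result is biased, or that the model would create associations. The documents do not support either: the primary tests do not use this model, and the bias is absent when there is no effect. A reader might also take the 20–48% failure rates as properties of the trial. They depend on carrier frequencies and a response rate that the plan does not give, and the plan does not commit to an adjusted model for every rare gene.

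**Conclusion.** The point holds as a minor, nearly free improvement. If ordinary maximum likelihood is used and a true effect exists, adjusted log odds ratios for 15–30% genes are inflated by about 6–9% with 3 covariates and 15–20% with 9–10. Coverage remains near nominal. For genes assumed at 5–10% carriers and 85% carrier response, no finite adjusted estimate exists in about 20–48% of trials.

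The conclusion rests on three assumptions: the covariate count, the rare-gene inputs, and reading unqualified logistic regression as the unpenalized kind. Section 14.2.3 counts PR in overall response, so responders may exceed 45. If all 125 patients were usable (about 56 responders), the zero-cell risk at 5% carriers and 80–90% carrier response would still be 29–54%.

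**What to change.** Replace the regression sentence in section 14.2.2 with text to this effect:

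*For each gene, the association with response will be adjusted by Firth penalized-likelihood logistic regression, with profile penalized-likelihood tests and 95% confidence intervals. Covariates are fixed in advance as [for example disease group, age and cytogenetic risk]. The number of carriers will be reported beside each estimate.*

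The investigators should choose the covariates and define their levels before response data are examined. Exact conditional logistic regression is not a good alternative, because it suits a continuous covariate such as age poorly. The chi-square and Fisher tests and the permutation step need no change for this purpose.

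The cost is a few lines of text and a method available in standard software, with no extra patients, samples or visits. Point estimates shrink slightly. For very rare genes the estimates become finite but stay imprecise and somewhat pulled toward the null, which the report should say.

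### The permutation rule for the primary analysis, as written, gives single-gene p-values without ties, so it does not deliver the promised multiplicity correction and is anti-conservative

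*Combined protocol and SAP*

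**What the plan says.** Section 14.2.2 (Primary Endpoint Analysis) tests each mutation against response in a contingency table, "assessed using Chi-square test or Fisher's exact test as appropriate". Four genes are named (DNMT3A, IDH1, IDH2, TET2), and the family is then left open: "Mutation rates in these genes and in other patient-specific genes will be correlated with overall response".

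The resulting P "values will be corrected for multiple testing". Bonferroni is set aside in favour of reshuffling who counts as a responder: "Since the Bonferroni correction is known to be too conservative, a permutation analysis (e.g., 10,000 random assignments for" response status). The only working definition is the sentence that follows: "The new critical p-value is the number of permutation tests which yield a lower p-value than the original test divided by the total number" of permutations. It cites reference 61, which in the reference list is a decitabine study in lung cancer.

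The section gives no minimum across genes, no treatment of ties and no rejection threshold for the permutation result. It calls that result a critical p-value, although a proportion of this kind is an empirical p-value. The earlier protocol versions in the same file carry the same rule in their Section 12.2.2. Section 14.2.3 relies on permutation for the secondary analyses without defining it further.

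**The concern.** There are two separate faults.

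- **No multiplicity correction.** Each gene's p-value is compared with the permuted p-values of that one test. Adding genes does not make the comparison stricter, so the familywise error grows as it would with no correction.
- **A strict count on discrete data.** A 2x2 table with fixed margins can take only a few values, so many permutations reproduce the observed p-value exactly. Leaving them out lowers the empirical p-value. With a continuous statistic and 10,000 permutations this would hardly matter; here it does.

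The rule decides which mutations are declared predictors of response, which is the primary objective. Section 14.2.2 says the aim is to find associations strong enough to justify testing patients before treatment, so a false predictor would have consequences.

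**Working it through.** **Inputs.** From Section 14.2.2: 100 evaluable patients, 45% overall response (45 responders), mutation frequencies of 15% to 30%, and alpha 0.05 in Table 3 but two-sided 0.10 in the text.

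**The plan's own power figure first.** With 20% carriers and a 30-point difference, the wild-type rate is 0.45 − 0.20 × 0.30 = 0.39 and the mutant rate is 0.69.
- Null SE = √(0.45 × 0.55 × (1/20 + 1/80)) = 0.1244.
- Alternative SE = √(0.69 × 0.31/20 + 0.39 × 0.61/80) = 0.1169.
- Power at two-sided 0.10 = Φ((0.30 − 1.645 × 0.1244)/0.1169) = 79.3%.

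This reproduces the stated 80%. It is a per-gene figure with no multiplicity adjustment.

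**False-positive rate for one gene.** Under no association, the number of responders among m carriers is hypergeometric (100 patients, 45 responders). Order the possible tables from most to least extreme by Fisher p-value. With ties counted, p is the probability of tables at least as extreme. Under the written rule, p is the probability of strictly more extreme tables only. The written rule therefore also rejects the first table whose tie-counted p exceeds 5%, and its true size is the next attainable level above 5%.

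| Carriers | Ties counted | As written |
|---|---|---|
| 15 | 4.8% | 9.2% |
| 20 | 4.9% | 7.7% |
| 30 | 2.7% | 5.3% |

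With one carrier, a responding carrier is the most extreme table, nothing is lower, and p = 0; this happens with probability 45/100 = 45%. With two carriers the rate is (45 × 44)/(100 × 99) = 20%. If chi-square supplies the ordering, the 15- and 20-carrier rates are unchanged and the 30-carrier rate becomes 7.8%.

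**Chance of at least one false positive**, genes assumed independent, 1 − Π(1 − size):
- Three groups (15, 20, 30 carriers): 1 − 0.908 × 0.9231 × 0.9472 = 21%.
- Four genes (15, 15, 20, 30 carriers): 1 − 0.908² × 0.9231 × 0.9472 = 28%.
- The same four genes with ties counted but still one gene at a time: 1 − 0.9518² × 0.9508 × 0.9726 = 16%.
- An illustrative 24 genes, all with 20 carriers: 1 − 0.9231²⁴ = 85%.

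**Simulation** (Fisher tests, 999 permutations, independent genes, no true association). For four genes with expected frequencies of 15% to 20%, familywise error at nominal 5% was:
- 27% under the written rule;
- 15% with unadjusted Fisher tests;
- 4.3% with min-p counting ties.

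For 24 genes, the written rule gave 83% to 98% depending on the assumed frequencies; min-p gave 4.1% to 5.0%.

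**Power after control** (Bonferroni as a guide; min-p is equal or somewhat better). At 0.10/4 = 0.025, power = Φ((0.30 − 2.241 × 0.1244)/0.1169) = 57%.

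**The case against.** The strongest reply is that min-p was meant. The plan says plainly that it will correct for multiplicity. A text on resampling-based multiple testing appears as reference 65 in the earliest version's list, so citation 61 may simply be misnumbered. The current list as available for review stops at 63 although the text cites up to 69, so that reference may stand there too. If each permutation contributed its smallest p-value across genes, even the strict count would do little harm: simulated familywise error was 5.0% to 6.4% at nominal 5%. This shows that the intention may have been sound. It does not rescue the sentence, which compares against one test and mentions no minimum. A programmer following it would code the faulty rule.

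Two further points stand:
- Section 14.2.2 gives the 15% to 30% frequencies for DNMT3A, IDH1/2 and TET2, which is three groups. The 21% figure fits that reading best.
- At 30 carriers the Fisher rate of 5.3% is close to nominal, and the 45% and 20% rates arise only if genes seen in one or two patients are formally tested. The plan does not say that they will be.

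A reader might infer that the trial will almost certainly declare false predictors. The documents do not support that. The wording "We will assess mutations in at least 24 recurrently mutated genes" in Section 1.3 belongs to the mutation-clearance goal, not to the primary test. Section 14.2.2 gives no number for its other genes, and the 85% rests on assumed carrier counts, independence and a global null.

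**Conclusion.** The point holds for the rule as written: it provides no multiplicity correction, and the strict count makes it worse than unadjusted Fisher tests. At nominal 5%, the familywise error is about 21% for three gene groups and 28% for four genes, given 100 patients, 45 responders, independent genes and Fisher ordering. With chi-square ordering the same products give 23% and 30%. Testing more genes raises the error, but its size cannot be fixed until the family is defined.

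It would go too far to say that no valid method was intended; the available evidence is compatible with min-p. It would also go too far to treat a 24-gene error rate as a property of this plan. The fault is a stated rule that gives the wrong answer for the primary objective, and it is easily repaired.

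**What to change.** Replace the sentence in Section 14.2.2 with a min-p (Westfall-Young) rule:
- List the genes or gene groups in the family, and say whether IDH1 and IDH2 are pooled.
- In each of B permutations of response, recompute every p-value in the family and keep the smallest.
- Set adjusted p = (1 + number of permutations with min p ≤ observed p)/(B + 1).
- Reject at one stated alpha. The text's 0.10 and Table 3's 0.05 must be reconciled.
- Report genes with very few carriers descriptively.
- Point the citation to the resampling multiple-testing reference, and let Section 14.2.3 refer to the same definition.

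State next to the 80% that it is per gene and unadjusted, and give the figure after control (roughly 57% for four genes at alpha 0.10). The exact carrier minimum, and whether to permute within AML and MDS, are optional choices.

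The change costs a paragraph of SAP text and a few lines of code, with no effect on trial conduct. The real price is power: fewer genes will reach significance, and the plan should say so.

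### The 80% power in Section 14.2.2 is for one uncorrected single-gene test, quoted at two alphas, and is not the power of the multiplicity-corrected primary analysis

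*Combined protocol and SAP*

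**What the plan says.** All of this is in Section 14.2.2 (Primary Endpoint Analysis) of the current protocol.

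- **Test powered.** "A power analysis was performed using Chi-square test for the association between mutation and response to decitabine". This is one mutation against response; no adjustment is mentioned.
- **Common assumptions.** Table 3 is built "assuming an expected overall 45% CR/CRi rate and 80% power", with 100 evaluable patients.
- **First alpha.** The worked example begins "For an average of 20% frequency of a mutated gene" and concludes that "100 patients will provide 80% power to detect 30% difference at a 2-sided 0.1 alpha error".
- **Second alpha.** The title of Table 3 reads "Detectable mutation associated response rates (80% power" and goes on to give alpha as 0.05, without saying one- or two-sided. Its 20% row lists a detectable difference of 0.35.
- **Planned analysis.** The critical P "values will be corrected for multiple testing". The method is permutation: "Since the Bonferroni correction is known to be too conservative, a permutation analysis" of response status is used. The genes in scope are DNMT3A, IDH1, IDH2 and TET2 in particular, plus other genes found mutated.

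The section gives no number of genes in the family, no family-wise alpha and no power after correction.

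**The concern.** The same section contains two design levels for the same primary question. A reader cannot tell whether 0.05 or 0.10 is the threshold for declaring that a gene predicts response. Neither level is the one at which a single gene would be judged once the correction is applied, because a correction over several genes makes the per-gene threshold stricter than the nominal alpha.

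The section says the study is meant to show whether any mutation merits testing before treatment. A null result would be read against the stated 80% power. If the corrected power is nearer one half, that null result is much weaker evidence of no association than it appears. A positive result has the opposite problem: its threshold can be chosen afterwards.

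**Working it through.** **Inputs from Section 14.2.2.** N = 100; overall response 45%; mutation frequency f; difference d. Table 3's alpha is taken as two-sided.

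**Response rates.** Wild-type p2 = 0.45 − f·d; mutant p1 = p2 + d; group sizes n1 = 100f and n2 = 100(1 − f).

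**Formula.** Power ≈ Φ[(d − z·s0)/s1], where z is the two-sided normal critical value, s0 = √[0.45 × 0.55 × (1/n1 + 1/n2)] and s1 = √[p1(1 − p1)/n1 + p2(1 − p2)/n2]. Each result was also checked by exact enumeration of the Pearson chi-square test over both binomials.

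**Step 1: reproduce the text figure.** With f = 0.20 and d = 0.30, p2 = 0.39, p1 = 0.69, n1 = 20 and n2 = 80.

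- s0 = √(0.2475 × 0.0625) = 0.1244
- s1 = √(0.69 × 0.31/20 + 0.39 × 0.61/80) = 0.1169
- At alpha 0.10: (0.30 − 1.645 × 0.1244)/0.1169 = 0.816, giving 79.3% (exact 79.1%)

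The printed 80% is thus reproduced, but only uncorrected and at 0.10.

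**Step 2: same effect at other levels.** The corrected levels assume four genes. Dividing alpha by 4 (Bonferroni) stands in for a minimum-p threshold. The last column is a simulated max-statistic permutation test with independent genes of equal frequency and one true effect; its Monte Carlo error is about 1.5 points.

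| Level for one gene | Formula | Exact | Permutation |
|---|---|---|---|
| 0.10 uncorrected | 79% | 79% | – |
| 0.05 uncorrected | 68% | 69% | – |
| 0.10/4 = 0.025 | 57% | 58% | 53% |
| 0.05/4 = 0.0125 | 46% | 49% | 41-43% |

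**Step 3: Table 3 rows.** Power is shown as formula / exact. The last two columns solve the formula for d at 80% power.

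| f | Printed d | Power at 0.05 | Power at 0.0125 | d at 0.05 | d at 0.0125 |
|---|---|---|---|---|---|
| 15% | 0.40 | 86 / 86% | 67 / 68% | 0.375 | 0.44 |
| 20% | 0.35 | 83 / 83% | 64 / 66% | 0.34 | 0.40 |
| 30% | 0.30 | 80 / 80% | 61 / 62% | 0.30 | 0.36 |
| 40% | 0.27 | 76 / 78% | 57 / 58% | 0.28 | 0.335 |
| 50% | 0.26 | 75 / 77% | 55 / 55% | 0.275 | 0.33 |

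Permutation over four genes at family-wise 0.05 gave 65%, 61% and 58% for the first three rows. The 15, 20 and 30% rows meet 80% at uncorrected 0.05. The 40 and 50% rows do not: exact power is 77.5% and 76.8%.

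**Step 4: the correction as written.** The section defines the corrected value as the share of permutations whose p-value falls below that of the test being adjusted. It does not say that each permutation contributes its smallest p over all genes. Read literally, this is a per-gene permutation p-value. Simulated power for the text effect is then 82-84% at 0.10 and 72-74% at 0.05, and there is no control across genes.

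**The case against.** **The arithmetic is mostly sound.** Each alpha roughly fits its own difference: 30 points at 0.10, 35 points at 0.05. Three of the five Table 3 rows reach 80%, and the two that miss lie outside the 15-30% frequency range the section cites for these genes. This stands. The fault is an unfixed alpha and power stated for a different test from the one planned; the table is not miscalculated throughout.

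**Permutation was chosen because Bonferroni is conservative.** With independent genes of equal frequency, the max-statistic permutation gave no gain over alpha/4. Correlated genes could recover some power, but the plan does not show this.

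**Perhaps no family-wise correction was meant.** The formula allows that reading, but the text promises a correction, and a textbook on resampling-based multiple testing is entry 65 in the reference list at the end of the combined document. If the literal formula were used, the power figure would survive and the promised correction would not.

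**All 125 enrolled patients might be evaluable.** The text effect would then have 87% power at 0.10 and 78% at 0.05 uncorrected, but 58% at 0.0125.

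**Stronger readings a reader might infer.**

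- *Power falls to 40% or lower because at least 24 genes are tested.* That list belongs to the mutation-clearance correlate in Section 1.3, and the primary section does not adopt it as the family. Dividing by 24 also assumes the genes are about equally common. In a simulation with four genes at 20% and an assumed twenty at 5%, minimum-p power was about 57% for 35 points and 40% for 30 points, close to the four-gene results of 60% and 41%.
- *A 30-point difference is undetectable at any tabulated frequency.* This depends on the chosen level. With IDH1 and IDH2 pooled (three genes) and family-wise 0.10, the per-gene level is 0.033, and exact power for 30 points is 80.5% at 40% frequency and 82.9% at 50%.
- *Thirty points is the sponsor's stated clinical threshold.* The cut-off is worded as a share of response attributable to a mutation; the 30-point difference is only the worked example.

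**Conclusion.** The point holds in this form: the 80% applies to one uncorrected test at either of two alphas, while the primary analysis is to be corrected over several genes. The documents do not determine the corrected power. Under an assumed family of four genes, it is about 41-49% for the text effect and 55-68% for the Table 3 effects at family-wise 0.05. At family-wise 0.10, the text effect has about 53-58%. These figures also assume a genuine minimum-p correction, approximated by alpha/4 or simulated with independent, equally common genes. A single headline range for the study's delivered power would go beyond what the documents support.

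The shortfall in the 40% and 50% rows of Table 3 is separate and small: about 3 points of power, or 0.01 to 0.015 in the detectable difference.

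**What to change.** In Section 14.2.2:

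1. State one family-wise alpha for the primary analysis.
2. Name the primary gene family and say whether IDH1 and IDH2 are pooled. The four named genes are one reasonable choice, with all other genes labelled exploratory.
3. State that each permutation contributes the minimum p over that family, and reword the formula to match.
4. Recompute Table 3 at the corrected level, stating sidedness. This also corrects the 40% and 50% rows, which need about 0.28 and 0.275 if uncorrected 0.05 is kept for reference.
5. Delete the 0.10 sentence, or restate it at the chosen level.

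N need not change. The cost is wording and one recalculated table. The downside is that the stated detectable differences look less favourable, and naming a primary family narrows which genes can support a confirmatory claim.
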